3.0 PATIENT SELECTION CRITERIA

Inclusion criteria:

Adult (aged 18 or above) of both sexes

Ischemic or non-ischemic cause of heart failure

QRS duration > 120 ms, non -LBBB type of conduction disturbance

NYHA class III or above

Sinus rhythm

Informed consent by the patient

Already received stable dose of guideline directed medical therapy for at least 3 months

Exclusion criteria

LBBB* patients

Pregnant women

Participation in another study

Patient with contraindication to left ventricle catheterization by a retrograde aortic approach (eg mechanical aortic valve, severe aortic stenosis and aortic dissection)

*The definitions of LBBB (QRS duration \geq 130 ms; QS or rS in lead V1; broad R waves in leads I, aVL, V5, or V6; and absent q waves in leads I, V5, and V6).

4.0 STUDY DESIGN

This is a prospective, single-center, non-randomized study, aiming to demonstrate the feasibility of tailor-made CRT delivery to optimize electrical dyssynchrony correction using noninvasive study of electrical activation in subgroup of patients with poor response to CRT.

Study will be performed in accordance with Declaration of Helsinki.

Recruitment Method

Patients with relative narrow QRS complex and non-LBBB pattern of conduction disturbance who is referred for CRT therapy will be recruited for the study. The clinical care of the patients recruited will not be different to other patients receiving CRT. The study will be carried out in Prince of Wales Hospital, Hong Kong.

5.0 STATISTICAL CONSIDERATION

Hypothesis

The null and alternative hypotheses are as follows:

H0: The responder rate of tailor-made approach \leq 40%

HA: The responder rate of tailor-made approach $>$ 40%

Sample size was calculated employing binomial methods with the following assumptions were used:

Expected responder rate for tailor-made approach =60%

Historical control responder rate =40%

Test significance level (a) = 0.05 (1-sided)

Power= 80%

Based on the above assumptions, the sample size was calculated as 77. Accounting for the attrition of 20%, the total required sample size is 93 patients with device implanted.

Statistical method for additional analysis

All continuous data will be summarized with the number of non-missing data, mean \pm standard deviation, median and range (minimum – maximum). T test will be used for the comparison between the groups. In case the assumption for t test is violated, then the equivalent nonparametric test, such as Wilcoxon rank sum test, Kolmogorov-smirnov test, will be used instead. The normality assumption will be tested by the normality test with the aid of QQ plot.

All categorical data will be tabulated with number of occurrence and percentage. Chi-square test will be used for the comparison between the groups. In case the expected counts in each cell is less than 5, then Fisher's exact test will be used instead.

Procedures for reporting any deviation(s) from the original statistical plan

Any deviations from the statistical analysis plan will be documented.

The treatment of missing, unused or spurious data, including drop-outs and withdrawals.

No imputation techniques will be used.

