2.0 STUDY OBJECTIVES

The purpose is to prospectively study the feasibility to optimize configuration of CRT delivery for acute correction of electrical dyssynchrony using a noninvasive mapping of global electrical activation.

Study Hypothesis

Tailor-made configuration of CRT delivery is feasible and able to improve responder rate compare to single method of CRT delivery in candidates with known poor response to CRT.

Primary outcome measure

Responder rate of greater than 10% of LV end systolic volume reduction in patients undergoing tailor-made approach of CRT delivery at 6 months. The responder rate is to compare with pre-defined level of 40% for single method of CRT delivery namely biventricular pacing with LV lead in coronary sinus.

Secondary outcome measures

1. The acute electrical dyssynchrony indices of different methods of CRT delivery.
2. The hemodynamic responses of different methods of CRT delivery.
3. Procedure duration and implantation success rate of the optimal CRT delivery method as determined by the best improvement in electrical dyssynchrony indices.
4. Cine images (PA, LAO 30°, RAO 30°) and Chest X ray (PA view)
5. Peri-operative and 6 months follow-up complications rate:
 - a. Thromboembolic event
 - b. Dislodgement and migration of pacing leads
 - c. Phrenic nerve stimulation
 - d. Others
6. Echocardiogram parameters at baseline and 6 months: left ventricular systolic and diastolic volume, left ventricular ejection fraction, degree of mitral regurgitation, strain imaging.
7. NYHA class, 6 minute hall walk test and quality of life using Minnesota's questionnaire at baseline and 6 months.
8. Electrical parameters including threshold, sensitivity and lead impedance of pacing leads at implant and 6 months follow-up.

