6.0 PROTOCOL DESCRIPTION

Patient informed consent

The investigator is responsible for obtaining informed consent from each prospective study patient prior to the performance of any study related procedures. After a patient has been provided with the information of the study and given time to think on whether to participating into the study, the patient will be asked to sign and date a consent form. One copy of the signed patient consent form must be handed out to the patient and one must be filed by the investigator in the investigator files. After the patient and the investigator have signed and dated the consent form, the study data collection process may start.

Patients meeting all the inclusion criteria and not meeting any of the exclusion criteria are eligible for the study. Data will be collected at the following study visits:

Enrollment

Noninvasive electrical activation and acute hemodynamic study

Implant

[figure not shown]
Pre-discharge (PDH) (\leq 72 hours post implant)

Month 3 follow-up visit: 90 ± 14 days post implant

Month 6 follow-up visit: 180 ± 14 days post implant

Table 1. Data collection for each scheduled visit

	Enrollment	Implant *	PDH*	Month 3	Month 6
Patient Informed Consent	x				
Echocardiogram	x		x	x	x
Medical History	x				
Cardiovascular Medication	x	x	x	x	x
NYHA Class	x			x	x
6MHW	x			x	x
SF-36QoL	x			x	x
12-lead electrocardiogram	x	x		x	x
Cine images		x			
Device Interrogation		x	x	x	x
Adverse Event	x	x	x	x	x
Protocol Deviation	x	x	x	x	x

Figure 1. Study Flow Chart

Noninvasive mapping of electrical activation

Ventricular activation maps will be acquired simultaneously with hemodynamic measurements using noninvasive mapping system (ECVUE, Medtronic Inc, USA). A thoracic computed tomographic scan will be acquired with the electrodes attached to the patient. Local ventricular activation times will be defined as the onset of the QRS complex or the pacing spike to the maximal negative slope of each unipolar electrogram.

The following electrical dyssynchrony indices will be derived

- i) Total activation time (TAT) is defined as the time difference between the earliest and latest site of activation on the entire ventricular epicardium (LV and RV);
- ii) RVTAT is defined as the time difference between the earliest and latest site of activation on the RV ventricular epicardium;
- iii) LVTAT is defined as the time difference between the earliest and latest site of activation on the LV ventricular epicardium;

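### The sample size of 77 does not follow from the stated one-sample test: the stated inputs need 42 to 44 evaluable patients, and 77 gives about 96% power rather than 80%

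*Combined protocol and SAP*

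**What the plan says.** The design has one treated group and a fixed reference. Section 4.0 says: "This is a prospective, single-center, non-randomized study". Section 2.0, under the primary outcome, says: "The responder rate is to compare with pre-defined level of 40% for single method of CRT delivery". Section 5.0 accordingly sets a null hypothesis of a responder rate of 40% or less against an alternative above 40%.

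The sizing inputs in Section 5.0 are an expected rate of 60%, a historical control rate of 40%, one-sided alpha of 0.05 and 80% power. On method it says only: "Sample size was calculated employing binomial methods with the following assumptions were used". The result is "Based on the above assumptions, the sample size was calculated as 77", followed by "Accounting for the attrition of 20%, the total required sample size is 93 patients with device implanted".

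No test is named for the primary outcome. The tests for categorical data appear under the additional-analysis subheading and are for groups: "Chi-square test will be used for the comparison between the groups". On missing data the section says: "No imputation techniques will be used".

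**The concern.** A rate compared with a constant needs far fewer patients than a rate compared with another sampled rate, because the constant has no sampling variance. For a 20-point difference around 50%, at one-sided 0.05 and 80% power, a one-sample test should need about 40 patients. A figure of 77 is nearly twice that, which suggests that a two-group formula was used.

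Two things are at stake. The first is whether N and the stated power describe the test that will be done; an ethics committee reading 80% power would be misinformed about why 93 patients are required. The second is exposure. Each added participant has the study-specific procedures: "A thoracic computed tomographic scan will be acquired with the electrodes attached to the patient", then multi-site pacing catheters and an invasive LV pressure measurement. Section 6.0 itself lists these as risks beyond those of a CRT implant. Because some participants may receive a conventional system, no extra exposure to non-standard leads is claimed.

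**Working it through.** **Inputs (Section 5.0).** p0 = 0.40, p1 = 0.60, one-sided alpha = 0.05 (z = 1.645), power 80% (z = 0.842), attrition 20%. Note p0(1−p0) = p1(1−p1) = 0.24, and the difference is 0.20.

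**1. Trying to reproduce 77 with the stated one-sample test.**

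- Normal approximation: n = (1.645 + 0.842)² × 0.24 / 0.20² = 37.1, so 38.
- Arcsine: effect h = 2·arcsin√0.6 − 2·arcsin√0.4 = 0.4027; n = (2.4865 / 0.4027)² = 38.1, so 39.
- Continuity-corrected normal: 41.9, so 42.
- Exact binomial: for each n, take the smallest r with P(X ≥ r | 0.40) ≤ 0.05, then compute P(X ≥ r | 0.60).

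| n evaluable | Reject if responders ≥ | Actual alpha | Power at 60% | Power at 55% |
|---|---|---|---|---|
| 42 | 23 | 0.0375 | 80.3% | 57.6% |
| 43 | 24 | 0.0260 | 76.4% | 52.0% |
| 44 | 24 | 0.0359 | 81.4% | 58.6% |
| 74 | 38 | 0.0314 | 94.8% | 77.3% |
| 77 | 39 | 0.0376 | 96.2% | 81.1% |

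The first n reaching 80% is 42. Power dips at 43 and does not fall below 80% from 44 on.

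- If the test were two-sided at 0.05: 47.1, so 48 (normal), or 49 (exact at 0.025 per side).

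No one-sample method at 80% power comes near 77.

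**2. What does give 77.** Two-sample comparison of 0.40 with 0.60, per group:

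- Pooled variance: (1.645·√0.50 + 0.842·√0.48)² / 0.04 = 76.23, so 77.
- Arcsine: 2 × 38.12 = 76.24, so 77.
- Unpooled: 74.19, so 75. Continuity-corrected: 85.94, so 86.

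The two-sample pooled or arcsine formula is the likely source. The documents do not say so.

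**3. The attrition step.** 77 × 1.2 = 92.4, so 93, which is the plan's figure. But 93 × 0.8 = 74.4, so about 74 remain. To retain 77 would need 77 / 0.8 = 96.25, so 97 implants. The effect on power at 60% is small: 96.2% to 94.8%.

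**4. Implants needed for the stated 80% power.** 42 / 0.8 = 52.5, so 53; 44 / 0.8 = 55. Against 93 planned, the excess is 93 − 55 = 38 to 93 − 53 = 40 patients.

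**5. Allowing attrition to vary.** Let each implanted patient be evaluable with probability 0.8, and take the critical value at the realised n. With 93 implants the mean power is 95.8% at a true 60% and 80.3% at 55%, with mean alpha 0.040. With 53 implants the mean power at 60% is 79.3%; with 54 it is 80.2%; with 55 it is 81.1%. So 55 is the safer figure for a smaller study.

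**The case against.** The strongest reply is that nothing the trial will conclude is threatened. The hypothesis, alpha and the 40% threshold are untouched, and the trial has more power than it claims. This stands, and it limits the weight of the point.

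Next, the additional patients are not wasted. With 74 evaluable the trial has 77.3% power if the true rate is only 55%, against 57.6% with 42. The complication data also gain: the upper 95% bound for a complication seen in nobody is 1 − 0.05^(1/93) = 3.2% with 93 implants, against 1 − 0.05^(1/53) = 5.5% with 53. This also stands, but the protocol gives none of these reasons. It presents 93 as what its stated inputs require.

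A third reply is that the chi-square sentence covers additional analyses only, and that the wording on binomial methods with a one-sided null points to a one-sample binomial test. That is a fair reading. It supports the recalculation above, and it still leaves the primary test unnamed.

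Finally, a smaller study is safe only if patients without a 6-month result are excluded from the denominator. Section 5.0 rules out imputation but does not define the analysis set. If the 20% lost were instead counted as non-responders (an assumption), a true 60% would become 0.8 × 60% = 48%, and exact power would be about 43% with 93 implants and about 29% with 53 or 55. This stands as a caution against cutting the sample before the analysis set is defined. It does not rescue the derivation of 77.

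**Conclusion.** The point holds. The stated inputs give 42 to 44 evaluable patients by the exact one-sample test (38 to 42 across the usual one-sided one-sample formulas), not 77. At 77 the power is 96.2%, about 16 points above the stated 80%. The attrition step is a further small slip, leaving about 74 evaluable and 94.8% power; it adds little.

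The error is conservative for the stated one-sample test. It would not be if a two-sample comparison were really intended, since 77 would then fill only one group; nothing in the documents describes a second group. The practical consequence is a wrong power statement and about 38 to 40 implants, with their study procedures, that the stated derivation does not support.

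These figures assume that only patients with a 6-month result are analysed and that the critical value is set at the number actually evaluable. The paragraph should be corrected; the trial's validity does not depend on it.

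**What to change.** Preferred: reword the sample-size paragraph and keep 93 implants. Suggested text:

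> The primary analysis is a one-sample exact binomial test of a responder rate of 40% or less, at one-sided 0.05, with the critical value determined at the realised number of evaluable patients. Ninety-three patients will be implanted. With 20% attrition about 74 will be evaluable, giving exact power of about 95% if the true rate is 60% and about 77% if it is 55%.

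Define the evaluable set in the same paragraph. The rule at 74 evaluable (38 or more responders) may be given as an illustration but must not be a fixed cut-off: 38 responders corresponds to alpha of 0.031 at n = 74, 0.061 at n = 77 and 0.105 at n = 80. This option costs one reworded paragraph. It adds no patients and changes no conduct.

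Alternative: re-derive N as 44 evaluable and 55 implanted, using n / (1 − 0.20). This reduces exposure but accepts about 58% to 59% power at a true 55%. It also gives a wider interval: with 42 to 44 evaluable at a 60% rate, the 95% half-width 1.96·√(0.24/n) is 14.8 to 14.5 points, against 11.2 at n = 74. Rare complications would be bounded less tightly. It should be considered only once the analysis set is defined.

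### The 93 implanted patients match 77 × 1.2; at the plan's own 20% attrition they leave about 74 evaluable, not 77 (77 / 0.8 gives 97).

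*Combined protocol and SAP*

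**What the plan says.** Section 5.0 (Statistical Consideration) tests a responder rate against a fixed 40%, assuming a true rate of 60%, one-sided significance of 0.05 and 80% power. It reports: "Based on the above assumptions, the sample size was calculated as 77". The attrition step follows at once: "Accounting for the attrition of 20%, the total required sample size is 93 patients with device implanted". No inflation formula is shown, and attrition is not defined further.

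Two other provisions matter. The primary outcome in section 2.0 is a reduction in LV end-systolic volume of more than 10% at 6 months, so it depends on the Month 6 echocardiogram listed in Table 1 of section 6.0. Section 5.0 also rules out imputation, and no rule counts a patient without that echocardiogram as a non-responder.

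**The concern.** The natural reading is that 77 patients are needed for analysis and that 93 are implanted so that 77 remain after a 20% loss. A loss of 20% is a fraction of those who start, so the starting number must be the base divided by 0.80. Multiplying the base by 1.20 leaves only 0.80 × 1.20 = 96% of it, whatever the base is.

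With no imputation planned, each patient without a 6-month measurement appears to leave the analysed set, and nothing else in the plan makes up the loss. If attrition turned out exactly as assumed, the final report would show fewer analysed patients than the plan says it requires, a shortfall created by the plan's own arithmetic. The count also deserves to be right because, under section 6.0, each participant undergoes an invasive pacing and pressure study, a CT scan and a device implantation.

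**Working it through.** **Inputs (all from section 5.0).** Base size 77; attrition 20%; stated total 93 implanted; null rate 0.40; expected rate 0.60; one-sided 0.05; power 80%. Section 4.0 gives the design: "This is a prospective, single-center, non-randomized study".

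**1. Reproduce the stated total.** 77 × (1 + 0.20) = 92.4, rounded up to 93. This is an exact match.

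**2. Apply the attrition to it.** 93 × (1 − 0.20) = 74.4, so about 74 patients remain. The shortfall against 77 is 2.6 expected patients, or 3 in whole patients.

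**3. Inflate by division.** 77 / (1 − 0.20) = 96.25, rounded up to 97. Check: 97 × 0.80 = 77.6, which is enough; 96 × 0.80 = 76.8, which is not. The gap from 93 is 4 implants, so rounding does not explain it.

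**4. Attrition that 93 does cover.** 1 − 77/93 = 16/93 = 17.2%.

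**5. Effect on power for the stated single-arm hypothesis.** The exact binomial test rejects at the smallest r for which P(X ≥ r | n, 0.40) ≤ 0.05; power is P(X ≥ r | n, 0.60).

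| Evaluable n | Reject at | Exact size | Exact power |
|---|---|---|---|
| 74 | ≥ 38 | 0.031 | 94.8% |
| 77 | ≥ 39 | 0.038 | 96.2% |

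**6. Where 77 may come from.** Section 5.0 says only that binomial methods were used. A one-sided comparison of two independent proportions gives, per arm, [1.645 × √(2 × 0.5 × 0.5) + 0.842 × √(0.4 × 0.6 + 0.6 × 0.4)]² / 0.20² = 76.2, rounded up to 77. The match is exact, but the source is an inference. On that formula, power is 80.4% at n = 77 and 78.9% at n = 74, just under the target.

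**7. Single-arm requirement for 80% power.** Exact power is 80.3% at n = 42, 76.4% at n = 43 and 81.4% at n = 44, and it stays at or above 80% from 44 onward. Dividing by 0.80 gives 42 / 0.80 = 52.5, so 53 implants, or 44 / 0.80 = 55 implants.

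**The case against.** Four points can be made for leaving the figure alone.

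- **It changes no decision.** Power is about 95% against a target of 80%, and the 20% is a planning guess given without a source, so 17.2% is probably within its uncertainty. The point about power stands, and it is why no additional enrolment is proposed. It does not make the sentence correct.
- **Attrition might mean 20% of the 77 completers.** That reading would rescue 93, but nothing in the documents supports it, and the text attaches the allowance to a total of implanted patients. If it was intended, the sentence still needs to say so.
- **The base is the larger problem.** If 77 is replaced, the figures 93, 97 and 74 all go with it. This is fair: changing 93 to 97 would agree with 77 without making 77 fit a single-arm test. What survives any change of base is the rule of dividing by 0.80.
- **The multiplication by 1.2 is inferred.** Section 5.0 shows no formula and does not use the word evaluable. That is true, but step 2 does not depend on how 93 was reached: 20% lost from 93 leaves 74.4.

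**Conclusion.** The concern holds. The stated 93 implanted patients do not preserve 77 at the stated 20% attrition: they leave about 74, and 97 would be needed. The error amounts to 4 implants, or two to three evaluable patients. It does not leave the trial underpowered for its stated hypothesis, where exact power is 94.8% with 74 patients.

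This rests on two assumptions: that attrition is a proportion of those implanted, and that patients without a 6-month echocardiogram drop out of the primary analysis, as the absence of imputation implies. The attrition figures take 77 as given. The power figures assume an exact one-sided binomial test; section 5.0 says "Sample size was calculated employing binomial methods with the following assumptions were used" but does not name the exact test.

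**What to change.** Reword the attrition sentence in section 5.0 without enrolling more patients. The better option keeps the 20% assumption and states what follows from it: 93 implanted patients leave about 74 evaluable, with exact power of about 95%. The alternative is to say that 93 allows for attrition of about 17%, which is sound only if the sponsor has reason to expect that rate.

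In the same edit, state the formula behind 77. If the base is re-derived for the single-arm test, divide the new number by 0.80. The smallest exact size reaching 80% power is 42 (53 implants); 44 evaluable (55 implants) is the safer figure because power dips below 80% at 43.

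The cost is one sentence, or a short paragraph if 77 is re-derived as well. No extra patients or procedures are required.

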Previous study on noninvasive activation pattern has shown that responders showed higher degree of baseline dyssynchrony and greater improvement of dyssynchrony by CRT when compared to nonresponders.¹⁷⁻¹⁹ The optimal configuration of CRT delivery is defined by that result in the greatest improvement of electrical dyssynchrony. The acute change in electrical dyssynchrony indices will be compare between the optimal configuration and the conventional configuration, namely biventricular pacing with single LV lead in posterior or lateral branch of coronary sinus. A significant different between the two configurations would suggest that there indeed is an optimal configuration of CRT delivery and a tailor made strategy is feasible. To prove this concept of tailor made strategy, devices will be implanted to deliver CRT using the optimal configuration determined by noninvasive electrical activation mapping in non-LBBB patients. The medium term improvement of surrogate marker of LV systolic volume will be compared to that of a predefined level of 40%.

Our group has been using echocardiogram to study mechanical dyssynchrony in patients with heart failure and pacing induced LV dysfunction in predicting response to CRT.³¹⁻⁴⁷ However, in subsequent multi-center trial studying 12 different echocardiographic parameters of mechanical dyssynchrony in predicting CRT response, no single echocardiographic measure of dyssynchrony was shown to improve patient selection for CRT.⁴⁸ The results of the study further strengthen the concept that the response to conventional CRT therapy cannot be predicted by baseline dyssynchrony pattern. It is rather the degree of improvement from baseline that will predict response to CRT therapy. The degree of dyssynchrony improvement on the other hand is determined by the interaction of baseline electrical substrate and the activation change brings about by CRT. The electrical substrate is fixed but different configuration of CRT delivery, including different location of LV lead, can produce different changes in activation. In order to study the interaction of electrical substrate and change in activation brings about by CRT, a tool that allows global electrical mapping of both the LV and RV is considered to be important not only to elucidate important information like location of conduction block but also to study the interaction of the left and right ventricle.^{17-19,22}

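### Section 1.0 selects and tests the optimal configuration on the same dyssynchrony index, so significance there cannot support tailoring; section 5.0 also names no paired method for within-patient secondary comparisons

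*Combined protocol and SAP*

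**What the plan says.** **Selection and comparison (section 1.0).** The selection rule is: "The optimal configuration of CRT delivery is defined by that result in the greatest improvement of electrical dyssynchrony". The comparison follows directly: "The acute change in electrical dyssynchrony indices will be compare between the optimal configuration and the conventional configuration". The document then says that a significant difference "between the two configurations would suggest that there indeed is an optimal configuration of CRT delivery and a tailor made strategy is feasible". The next step in the same section is to implant the chosen configuration and compare the 6-month LV volume response with 40%; that step is the one described as proving the concept.

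Conventional biventricular pacing is configuration 1 in the list of configurations to be tested (section 6.0, catheter placement). Section 6.0 defines five dyssynchrony indices. No section says which of them, or what combination, picks the optimum, and no repeat map is described.

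**Tests (section 5.0, additional analysis).** For continuous data, "T test will be used for the comparison between the groups"; if its assumptions fail, an equivalent nonparametric test, "such as Wilcoxon rank sum test, Kolmogorov-smirnov test, will be used instead". For categorical data, "Chi-square test will be used for the comparison between the groups", with Fisher's exact test for small expected counts. The groups are not defined. The study is one non-randomized cohort (section 4.0). The secondary outcomes in section 2.0 that imply a comparison (items 1, 2, 6, 7 and 8) set pacing methods against each other in the same patient, or an earlier visit against 6 months.

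**The concern.** The main issue is selection and testing on one set of measurements. If the best of several noisy readings is picked in each patient and then compared with one of those readings, the picked one looks better even when all configurations are equally good. A significant result would be obtained whether or not tailoring does anything, yet the plan would read it as support. Feasibility is the study's stated purpose, so this reading matters. Using a paired test does not help.

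The lesser issue is the choice of test. The phrase about groups and the named fallbacks point to independent samples, while the data are mostly paired. Ignoring positive correlation within patients inflates standard errors, so modest secondary changes could be missed. The two errors run in opposite directions.

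**Working it through.** **Inputs from the document.** The number of patients is 93: "Accounting for the attrition of 20%, the total required sample size is 93 patients with device implanted". It follows from 77 × 1.2 = 92.4, rounded up. Mapping precedes implant and attrition, so 93 is a reasonable number for the acute comparison. The number of candidate configurations K is given as 8 in one place in section 6.0 and 7 in another, which should be reconciled. K is one fewer where configuration 2 has the same site as configuration 1. I use K = 6, 7 and 8. The plan states no figure for these secondary analyses, so there is none to reproduce.

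**Assumptions.** The document gives no measurement noise, within-patient correlation or target change. For selection I take the limiting null: no true difference between configurations, one index, independent noise of equal SD. For pairing I take equal SDs at both occasions, a two-sided 5% test, r = 0.3, 0.5 and 0.7, and changes of 0.3 and 0.5 SD.

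**1. Selection effect.** Sign the readings so that larger means more improvement. For each patient, d = best of K readings − conventional reading.

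- Conventional is one of the K, so d ≥ 0 always.
- In units of the noise SD, the mean of d is the expected maximum of K standard normals: 1.27 (K = 6), 1.35 (K = 7), 1.42 (K = 8).
- The maximum has variance at most 1 and is not negatively correlated with the conventional reading, so the SD of d is at most √2 = 1.414.
- Paired t ≈ mean(d) / [SD(d)/√93], with √93 = 9.644. Lower bounds on its typical size:
  - K = 6: 1.27/1.414 × 9.644 = 8.7
  - K = 7: 1.35/1.414 × 9.644 = 9.2
  - K = 8: 1.42/1.414 × 9.644 = 9.7
- The critical value is about 2. Simulation gives rejection in 100% of runs for all three K. The noise SD cancels from t, so the result does not depend on it.
- An unpaired test does not escape: for K = 7 or 8 it rejects in at least 99% of runs for within-patient correlation up to 0.9.

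**2. Measures not used for selection.** The guarantee d ≥ 0 applies only to the selecting index. For another measure, such as LV dP/dt or a non-selecting index, the false rejection rate depends on how its noise correlates with that of the selecting index (n = 93, K = 6 to 8):

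| Assumed noise correlation | False rejection |
|---|---|
| 0 | about 5% |
| 0.1 | 16–18% |
| 0.2 | 47–54% |
| 0.3 | 82–88% |

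**3. Unpaired test on paired data.** The SE used is SD√(2/n). The true SE is SD√(2(1 − r)/n). The ratio 1/√(1 − r) is 1.20, 1.41 and 1.83 for r = 0.3, 0.5 and 0.7.

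For 0.3 SD, r = 0.5 and n = 77:

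- Paired: 0.3/√(1/77) = 2.63; power ≈ Φ(2.63 − 1.96) = 75% (simulation 74%).
- Unpaired: 0.3/√(2/77) = 1.86; the statistic has SD √0.5 = 0.707; power ≈ 1 − Φ((1.96 − 1.86)/0.707) = 44% (simulation 44%).

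Simulated power with 77 pairs, unpaired against paired:

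| Change | r = 0.3 | r = 0.5 | r = 0.7 |
|---|---|---|---|
| 0.3 SD | 45% v 59% | 44% v 74% | 42% v 92% |
| 0.5 SD | 91% v 96% | 94% v 99% | 98% v 100% |

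With 74 pairs (93 × 0.8 = 74.4), the largest loss at 0.5 SD is 98.9 − 93.2 = 5.7 points.

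**The case against.** **On selection.** The sentence sits in the Background, and neither section 2.0 nor section 5.0 lists optimal against conventional as a formal test. It says only that significance would *suggest* feasibility and keeps *prove* for the 6-month volume outcome. The null of no difference in any patient is extreme, and 10-second averaged recordings free of premature beats should reduce noise. The first two points stand and limit the harm. The last two limit the size of the bias in ms, which cannot be known from the document. They do not rescue the inference, because a result that is virtually certain under the null cannot suggest anything.

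A reader might infer that comparisons on all five indices are guaranteed to be significant, or that LV dP/dt is biased too. The document supports neither. The guarantee covers the selecting index alone. Simultaneous recording of maps and pressures (section 6.0) means that shared noise could arise, not that it does.

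**On pairing.** A reader might infer that section 5.0 prescribes unpaired tests for paired data. It does not: the t test is unqualified and the list of alternatives is open. Section 1.0 also speaks of patients with different patterns of activation delay, so a genuine between-patient comparison may be intended. If unpaired tests were run, they would be conservative, with no secondary power target to miss. All of this stands, which is why this part is minor.

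**Conclusion.** The selection point holds: as written, significance on the selecting index cannot support the conclusion that section 1.0 attaches to it. In the limiting null the apparent gain averages 1.27 to 1.42 noise SDs and rejection is essentially certain with 93 patients. This rests on one selecting index and independent equal noise; the certainty of rejection does not depend on the noise size.

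The pairing point is a clarification of supportive analyses. The power loss is sizeable at an assumed 0.3 SD change and at most about 6 points at 0.5 SD.

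It would be wrong to conclude that the trial's main result is compromised. The one-sample comparison of the 6-month responder rate with 40% uses neither these tests nor the selection index. Nor does pairing address informative dropout. The plan states "No imputation techniques will be used", and neither form of test cures that.

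**What to change.** 1. In section 1.0 or 5.0, state in advance which of the five indices, or what rule, selects the optimum.
2. Report optimal against conventional on that index descriptively (estimate and spread, no p-value), and remove the section 1.0 inference from its significance.
3. If LV dP/dt is compared between optimal and conventional, label it supportive and note that simultaneous recording could introduce shared noise. Apply the same caution to non-selecting indices.
4. In section 5.0, define the groups and keep the named independent-sample tests for stated between-patient contrasts, such as pattern of activation delay.
5. For two-occasion outcomes, name a paired t test, or the signed-rank test where differences are not normal or the scale is ordinal (NYHA class, mitral regurgitation grade). State the number of pairs for each analysis.
6. For indices and LV dP/dt across sinus rhythm and all configurations, name a repeated-measures method, such as a mixed model with a random patient effect.

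The cost is wording only, with the same data and no added patients or procedures. The one loss is a p-value that carried no information.
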